### **SAE Reporting:**

To ensure patient safety, every SAE, regardless of causality, occurring after the patient has provided informed consent and until 30-days after the subject stopped study participation must be reported to the Incyte as soon as possible but no later than 5 days from learning of its occurrence according to the Mayo Clinic IRB policy. Any SAEs experienced after the 30-days period should only be reported to Incyte and the Mayo Clinic IRB if the investigator suspects a causal relationship to study treatment. Recurrent episodes, complications, or progression of the initial SAE must be reported as follow-up to the original episode, regardless of when the event occurs. This report must be submitted as soon as possible but no later than 5 days from the investigator receiving the follow-up information. SAE should be followed up until resolution or until it is judged to be permanent. An SAE that is considered completely unrelated to a previously reported one should be reported separately as a new event.

Information collected on the adverse event worksheet (*and entered in the research database*):

- Subject's name:
- Medical record number:
- Disease/histology (if applicable):
- The date the adverse event occurred:
- Description of the adverse event:
- Relationship of the adverse event to the research (drug, procedure, or intervention\*):
- If the adverse event was expected:
- The severity of the adverse event: (use a table to define severity scale 1-5\*\*)
- If any intervention was necessary:

- Resolution: (was the incident resolved spontaneously, or after discontinuing treatment)
- Date of Resolution:

**AE Reporting:**

Its relationship to the:

- Study treatment (no/yes), or
- Investigational treatment (no/yes), or

- The other study treatment (non-investigational) (no/yes), or
- Both or indistinguishable

The relationship will be categorized as follows:

- Unrelated- Clearly due only to extraneous causes, and does not meet criteria listed under possible or probable.
- Unlikely- Does not follow a reasonable temporal sequence from administration. May have been produced by the patient's clinical state or by environmental factors or other therapies administered.
- Possible- Follows a reasonable temporal sequence from administration, but may have been also produced by the patient's clinical state, environmental factors or other therapies administered.
- Probable- Clear-cut temporal association with administration with improvement on cessation of investigational medicinal product or reduction in dose. Reappears upon rechallenge. Follows a known pattern of response to the investigational medicinal product.

Its duration (start and end dates) or if the event is ongoing an outcome of not recovered/not resolved should be reported.

Whether it constitutes a serious adverse event(SAE)

**Adverse Events (AE):**

The severity grade/Common Toxicity Criteria (CTC) AE Version 5.0 grade

- Mild: usually transient in nature and generally not interfering with normal activities
- Moderate: sufficiently discomforting to interfere with normal activities
- Severe: prevents normal activities

If CTCAE grading does not exist for an adverse event, use

1=mild, 2=moderate, 3=severe, 4=life-threatening, CTCAE Grade 5 (death) is not used, but is collected in other CRFs (Study Completion, Death/Survival).

### 8.3.2 Sponsor-Investigator reporting: Notifying the FDA and Funding Sponsor

The sponsor-investigator will report to the FDA all unexpected, serious suspected adverse reactions according to the required IND Safety Reporting timelines, formats and requirements.

Unexpected fatal or life threatening suspected adverse reactions where there is evidence to suggest a causal relationship between the study drug/placebo and the adverse event, will be reported as a serious suspected adverse reaction. This will be reported to the FDA on FDA Form 3500A, no later than 7 calendar days after the sponsor-investigator's initial receipt of the information about the event.

Other unexpected serious suspected adverse reactions where there is evidence to suggest a causal relationship between the study drug/placebo and the adverse event, will be reported as a serious suspected adverse reaction. This will be reported to the FDA on FDA Form 3500A, no later than 15 calendar days after the sponsor-investigator's initial receipt of the information about the event.

Any clinically important increase in the rate of serious suspected adverse reactions over those listed in the protocol or product insert will be reported as a serious suspected adverse reaction. This will be reported to the FDA on FDA Form 3500A no later than 15 calendar days after the sponsor-investigator's initial receipt of the information about the event.

Findings from other studies in human or animals that suggest a significant risk in humans exposed to the drug will be reported. This will be reported to the FDA on FDA Form 3500A, no later than 15 calendar days after the sponsor-investigators initial receipt of the information about the event.

### **SAE Reporting to the Sponsor (Incyte)**

Incyte needs to be notified within 24 hours of learning of an event. Incyte also needs to be provided a completed SAE form via email. SAE reporting for each subject begins the day the informed consent is signed by the patient and within 30 days after subject has completed or discontinued from the study or has taken last dose of the study drug, or as described in the IST protocol.

SAEs, occurring using Incyte Study drug, are reported in accordance with the effective protocol. SAEs occurring with any another commercial drug are reported to manufacturer of that drug in accordance with regulations and protocol.

Initial Serious Adverse events (SAEs) and/or subsequent follow-up reports should be reported via email to: [REDACTED] or fax [REDACTED]. SAE reports should be for a single subject. SAE forms will be e-mailed with a cover sheet and any additional attachments.

All adverse event information is reported to Incyte on the Principal Investigator's/Institution's Adverse Event Report Form, or a CIOMS-I or MedWatch Form FDA 3500A, or on an Adverse Event Report Form which may be provided by Incyte upon request. The Principal Investigator does not provide medical records (e.g., discharge summary) to Incyte, unless specifically requested.

Copies of IND safety reports submitted to the FDA by the Institution will be shared with the contact above so that these reports can be evaluated and included in investigator brochure or

Incyte IND safety submissions as required to ensure safety of other patients who are receiving the product from Incyte for sponsored trials.

### **Procedure for Reporting of Pregnancy and Lactation to the Sponsor (Incyte)**

An “Initial Pregnancy Report” or equivalent must be completed in full and emailed to [REDACTED], fax [REDACTED] within 24 hours of discovery of a pregnancy of a subject who has taken the Incyte product or the pregnancy of a partner for a subject who has taken the Incyte product. The “Follow-up Pregnancy Report Form” or equivalent must be completed and emailed to [REDACTED], fax [REDACTED] within 30 days after delivery, so that Incyte is provided with information regarding the outcome of the pregnancy. If the pregnancy results in any events which meet the serious criteria (i.e., miscarriage or termination), the SAE reporting process needs to be followed and the timelines associated with an SAE should be followed.

### **Stopping Rules**

The stopping rules specified below are based on the knowledge available at study development. The stopping rule applies to the overall study. We note that the Adverse Event Stopping Rule may be adjusted in the event of either (1) the study re-opening to accrual or (2) at any time during the conduct of the trial and in consideration of newly acquired information regarding the adverse event profile of the treatment(s) under investigation. The study team may choose to suspend accrual because of unexpected adverse event profiles that have not crossed the specified rule below.

Accrual will be temporarily suspended to this study if at any time we observe events considered at least possibly related to study treatment (i.e. an adverse event with attribute specified as “possible”, “probable”, or “definite”) that satisfy the following:

- If 2 or more patients in the first 6 treated patients (or 30% after the first 6 treated patients have been accrued) experience a grade 3 or higher non-hematologic adverse event.

We note that we will review grade 4 and 5 adverse events deemed “unrelated” or “unlikely to be related”, to verify their attribution and to monitor the emergence of a previously unrecognized treatment-related adverse event.

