## **1.5 Dose Rationale**

### Topical Dosing:

In addition to the safety pharmacology and toxicology studies that were completed to support development of ruxolitinib cream. The relative bioavailability of ruxolitinib cream was markedly (~ 90%) lower than that following oral administration. In vitro metabolism studies strongly suggest that cytochrome P450 (CYP) 3A4 is the predominant CYP isozyme responsible for the metabolism of Ruxolitinib cream. 1.5% ruxolitinib cream BID was generally found to be the most efficacious regimen in studies with AD and psoriasis (see below) and hence this regimen is also proposed for this trial.

Ruxolitinib cream has been evaluated in over 200 subjects with plaque psoriasis in 3 clinical studies with dosing of 1 to 3 months' duration. Study INCB 18424-201 was a double-blind, vehicle-controlled, rising-dose, safety, tolerability, PK, and preliminary efficacy study of INCB01824 1% cream applied QD and 1.5% cream applied BID. All adverse events (AEs) were mild to moderate in intensity and most judged unrelated to study medication, with no associated serious AEs (SAEs) or withdrawals. Laboratory and ECG evaluations did not suggest any safety issues, specifically no instances of neutropenia, thrombocytopenia, or leukopenia.

INCB 18424-202 was an open-label, multicenter, sequential-cohort, dose-escalation, safety, tolerability, PK, pharmacodynamics (PD), and preliminary efficacy study of Ruxolitinib cream 1.0% or 1.5% applied to 2% to 20% BSA QD or BID for 4 weeks. Application area increased sequentially, and alternative dosing paradigms were explored at the highest application area. The efficacy analyses collectively demonstrated efficacy of all 5 regimens of Ruxolitinib cream in psoriasis. The incidence of all reported AEs, the clinical laboratory results, vital signs, and ECG findings showed no confirmed safety signals or trends. Mean topical bioavailability ranged from 3.4% to 5.2% with no significant inhibition of cohort mean PD. Overall, Ruxolitinib cream (1.0% or 1.5%) was demonstrated to be safe and well tolerated when applied QD or BID for 28 days to plaque psoriasis affecting 2% to 20% of the BSA.

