## 1.6 Risks and Benefits

### Benefits:

Others with NL may benefit in the future from what we learn in this research study. It is possible their symptoms could also improve while being treated with this study drug

Risks:

The following adverse events were reported as very common Side effects associated with the use of Ruxolitinib cream:

- Very common (occurring in greater than or equal to 10% of subjects), common (occurring in 1-10% of subjects), and rare (occurring in 0.1% of subjects) side effects occurring in subjects. As of the clinical data cutoff date, 793 unique participants have been exposed to ruxolitinib cream and 515 participants have been randomized in ongoing blinded studies in AD, where participants receive 0.75% ruxolitinib or 1.5% ruxolitinib or vehicle in a 2:2:1 ratio. The most frequently reported TEAEs in healthy participants and participants with psoriasis, AA, AD, and vitiligo are listed below.

Indication	N	TEAEs by PT ( $\geq 6$ participants)
Healthy participants	41	No TEAEs at the time of data cutoff
Psoriasis	203	Upper respiratory tract infection, nasopharyngitis, application site irritation, headache, application site pruritus, abnormal ECG QT interval, pruritus, sinusitis
AA	83	Nasopharyngitis, pruritus, sinusitis
AD	314	Nasopharyngitis, upper respiratory tract infection, headache, atopic dermatitis
Vitiligo	152	Acne, viral upper respiratory tract infection, application site pruritus, pruritus, upper respiratory tract infection, sinusitis, bronchitis, influenza, oral herpes, application site erythema, diarrhea, headache, skin exfoliation

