**Very Common (affecting more than 10 in every 100 patients )**

Pruritus (itching)
Upper respiratory tract infection / nasopharyngitis (common cold)
Dry Skin
Headache
Acne
Application site redness / irritation

Common (affecting less than 10 in every 100 patients)	
Change in ECG tracing	Abdominal pain (stomach pain)
Sinusitis (sinus infection)	Muscle strain
Back Pain	Throat Pain
Diarrhea	Psoriasis (skin disorder under treatment)
Liver enzyme increased	Blood sugar increased
Gastroenteritis (vomiting/diarrhea caused by virus)	Cholelithiasis (stone in gall bladder)
Influenza (flu)	Cough / Bronchitis
Pneumonia (lung infection)	Cystitis (irritation of bladder)
Fever	Bulging disk in back
Skin peeling	Blood cell count decreased
Ear infection	Mouth pain
Atopic Dermatitis (treatable skin condition)	Urinary tract infection
Bursitis	Tendonitis
	Oral herpes

Rare but Serious
Asthma
Psychosis exacerbation (worsening delusions, paranoia)

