**Hematologic abnormalities:**

Ruxolitinib taken systemically can inhibit the growth of blood cells. Low blood cells can make subjects more susceptible to infections by bacteria, virus, and fungi. The risk is low with systemic therapy and was not noted with topical therapy but subjects will be monitored for any signs of inhibition of their blood counts.

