#### **8.3.1 Sponsor-Investigator reporting: notifying the Mayo IRB**

The sponsor-investigator will report to the Mayo IRB any UPIRTSOs and Non-UPIRTSOs according to the Mayo IRB Policy and Procedures.

Action taken regarding treatment

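### The only mandatory accrual-suspension rule leaves out hematologic events, so related grade 3-4 cytopenias cannot trip it: a low-probability gap that one separately counted criterion would close

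*Combined protocol and SAP*

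**What the plan says.** The Stopping Rules state that accrual will be suspended temporarily if events judged at least possibly related to treatment meet one criterion: 2 or more of the first 6 treated patients, or 30% after that, "experience a grade 3 or higher non-hematologic adverse event". There is no matching hematologic criterion anywhere in the document, and the section gives no specific reason for the restriction. It adds a discretionary route: "The study team may choose to suspend accrual because of unexpected adverse event profiles that have not crossed the specified rule below". The rule may also be adjusted in the light of new information.

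Section 1.6 (Hematologic abnormalities) says that systemic ruxolitinib can suppress blood cell growth, that the risk is low with systemic use and was not noted with topical use, and that "subjects will be monitored for any signs of inhibition of their blood counts". The side-effect list in the same section places "Blood cell count decreased" in its common band, headed as "affecting less than 10 in every 100 patients". Table-2 schedules a CBC at screening and at Weeks 1, 2, 3, 4, 8, 12 and 16.

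**The concern.** The protocol identifies a class effect of the drug, undertakes to watch for it and draws the blood to do so, but does not connect the results to its only mandatory study-level action. Two related grade 3 non-hematologic events in the first 6 subjects force a pause in enrolment. Two related grade 3-4 neutropenias in the same subjects do not: enrolment continues unless the team, or a body receiving the reports, decides otherwise. A later statement that the stopping rule was not crossed would also carry no direct information about blood counts. A reader could easily miss that.

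**Working it through.** **Step 1: can any other provision force a pause?**
- Discretionary suspension and rule adjustment (Stopping Rules): permitted, not required.
- Extra review of grade 4-5 events (Stopping Rules): covers only events deemed unrelated or unlikely to be related, so related cytopenias fall outside it.
- Treatment interruption or discontinuation (section 8.3.1, AE Action; section 3.6): acts on the individual subject.
- Abnormal Laboratory Values and the alert ranges in section 8.4: action is left to the investigator, and the protocol sets no numeric trigger.
- Reporting to the IRB (8.3.1: "The sponsor-investigator will report to the Mayo IRB any UPIRTSOs and Non-UPIRTSOs"), and to the FDA and Incyte (8.3.2): informs others. The FDA and Incyte routes depend on seriousness.
- Regular review of serious adverse events (8.4): has no pause attached.

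None requires accrual to stop for a cytopenia.

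**Step 2: operating characteristics.** The plan states none for this rule, so there is no figure to reproduce. Inputs from the documents are N = 12 (section 3.2) and the two thresholds. I read the 30% limit as events/n ≥ 0.30, with the smallest whole number meeting it:
- n ≤ 6: 2 events
- n = 7 to 10: 3 events (0.30 × 7 = 2.1; 0.30 × 10 = 3.0)
- n = 11 to 12: 4 events (0.30 × 11 = 3.3; 0.30 × 12 = 3.6)

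The rule is applied after each subject, with an exact binomial recursion carrying forward only the paths that have not yet crossed. Subjects and event types are taken as independent, and each outcome is assumed known before the next enrolment. Every true rate p below is an assumption.

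As written, P(suspension from cytopenias alone) = 0 for every p. With the same thresholds applied to hematologic events:

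| Assumed rate p of related grade 3+ hematologic events | P(cross by subject 12) |
|---|---|
| 1% | 0.15% |
| 2% | 0.60% |
| 5% | 3.65% |
| 10% | 13.6% |
| 20% | 43.1% |

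As a check on the first 6 at p = 5%: 1 − 0.95⁶ − 6 × 0.05 × 0.95⁵ = 3.3%. The remainder of the 3.65% comes from subjects 7 to 12. The 10% row uses the ceiling of the protocol's common band, which is not a grade 3+ rate. The 20% row is a stress case beyond any rate in the documents.

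**Step 3: cost of adding the criterion.** Let P_N and P_H be the crossing probabilities for non-hematologic and hematologic events.
- Separate counts: added chance = [1 − (1 − P_N)(1 − P_H)] − P_N = P_H(1 − P_N).
- One pooled count: per-subject rate = 1 − (1 − p_N)(1 − p_H), put through the same recursion, minus P_N.

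| Non-hematologic rate | P_N | Separate: added at hematologic 2% / 5% | Pooled: added at hematologic 2% / 5% |
|---|---|---|---|
| 0% | 0 | 0.6 / 3.7 points | same as separate |
| 5% | 3.65% | 0.6 / 3.5 points | 3.1 / 9.3 points |
| 10% | 13.6% | 0.5 / 3.2 points | 4.7 / 12.5 points |

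For example, at a 10% non-hematologic and 5% hematologic rate, separate counts add 0.0365 × (1 − 0.1361) = 0.0315. Pooling uses a per-subject rate of 1 − 0.90 × 0.95 = 0.145, which crosses with probability 0.2608, so it adds 0.2608 − 0.1361 = 0.1248.

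**The case against.** The strongest reply is that the exclusion is harmless. Section 1.6 says the effect was not noted topically. Section 1.5 reports, for one psoriasis study, "specifically no instances of neutropenia, thrombocytopenia, or leukopenia". Treatment is limited to 10% of body surface. This is a single-site, 12-subject trial in which the team that reads the CBCs also controls accrual. Section 8.1 treats an event as unanticipated when it is more frequent or more severe than expected. That definition is written for another purpose, but by the same logic grade 3-4 cytopenias would probably qualify for discretionary suspension. A pause in accrual protects only people not yet enrolled; treated subjects are protected by frequent CBCs and individual discontinuation.

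Most of this stands and limits the weight of the point. It does not close the gap: the protocol chose a mandatory trigger for non-hematologic events, and discretion does not replace one for hematologic events.

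Three stronger readings are tempting, and the documents support none of them.
- A reader might infer that cytopenias would go unseen. They would not: CBCs are scheduled throughout, and serious cases are reported. A related grade 3+ non-hematologic consequence, such as an infection, would also still count toward the existing rule.
- A reader might infer a likely hazard. The available data point the other way.
- A reader might use the adverse-event table in section 1.6 ("The most frequently reported TEAEs in healthy participants and participants with psoriasis, AA, AD, and vitiligo are listed below") to bound the risk. It lists terms seen in 6 or more participants and shows no blood-count term, which suggests at most 5 per term, or 5/314 = 1.6% in atopic dermatitis and 5/83 = 6.0% in alopecia areata. These are ceilings for single terms, at any grade and from any cause. Several terms could each fall below the cut-off, so they do not bound the rate for the whole hematologic class. Nor do they estimate related grade 3+ events.

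**Conclusion.** The point holds as a low-probability gap in a stated safety rule. On the wording, related grade 3-4 cytopenias have zero chance of triggering the mandatory suspension, and no other provision requires a pause. In practice the effect is small: at an assumed 1% rate a matching hematologic criterion would be crossed in 0.15% of such trials, and at 5% in 3.7%. The documents give no related grade 3+ hematologic rate, so these are illustrations over a range and not predictions. They also rest on independence and on each outcome being known before the next enrolment. No endpoint or estimate is affected. The change is recommended because it is cheap and makes the rule consistent with the monitoring the protocol already promises.

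**What to change.** Keep the existing criterion and add a second one, counted separately, with the same thresholds and the same at-least-possibly-related condition:
- **Events:** CTCAE 5.0 grade 3 or higher neutropenia, anemia, thrombocytopenia, leukopenia or lymphopenia on any CBC.
- **Baseline:** the grade must be worse than at screening.
- **Laboratory-only findings:** the event counts whether or not the value meets the conditions under Abnormal Laboratory Values for being documented as an adverse event. Without this, it is unclear whether an asymptomatic grade 3 value counts.

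Do not simply delete the word non-hematologic. Pooling both types in one count raises the chance of a needless pause by more, as shown above. If the sponsor prefers the exclusion, the reason should be stated in the Stopping Rules.

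The cost is one added criterion and an IRB submission, using CBCs already in Table-2. The added chance of a temporary suspension by subject 12 is about 0.5 to 3.7 points at assumed hematologic rates of 2% to 5%, or 0.15 points at 1% with no non-hematologic events. Some false alarms are possible beyond that: section 5.5 and the notes to Table-1 allow immunosuppressants for other conditions, and the protocol's possible category includes events that other therapies may have caused.

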### **8.4 Medical Monitoring**

It is the responsibility of the Principal Investigator to oversee the safety of the study at his/her site. This safety monitoring will include careful assessment and appropriate reporting of adverse events as noted above, as well as the construction and implementation of a site data and safety-monitoring plan (see section 10 “Study Monitoring, Auditing, and Inspecting”). Medical monitoring will include a regular assessment of the number and type of serious adverse events.

The occurrence of adverse events will be sought by non-directive questioning of the patient at each visit during the study. Adverse events also may be detected when the patient volunteers them during or between visits or through physical examination, laboratory test, or other assessments. Please see Supplemental 3 for a detailed description of safety monitoring. Clinically significant abnormal laboratory values or test results will be identified through a review of values outside of normal ranges/clinically notable ranges, significant changes from baseline or the previous visit, or values which are non-typical in patient with underlying disease. Investigators have the responsibility for managing the safety of individual patient and identifying adverse

events. Alert ranges for labs and other test abnormalities are included determined by the Mayo Clinic Arizona and Mayo Medical Laboratory. Adverse events will be recorded in the Adverse Events Case Report Form (CRF) under the signs, symptoms or diagnosis associated with them, and severity. All adverse events will be treated appropriately. Once an adverse event is detected, it should be followed until its resolution or until it is judged to be permanent, and assessment should be made at each visit (or more frequently, if necessary) of any changes in severity, the suspected relationship to the study drug, the interventions required to treat it, and the outcome (see Supplemental 3). Information about common side effects already known about the investigational drug can be found in the package insert. This information will be included in the patient informed consent and should be discussed with the patient during the study as needed. The investigator will also instruct each patient to report any new adverse event (beyond the protocol observation period) that the patient, or the patient's personal physician, believes might reasonably be related to study treatment. This information should be recorded in the investigator's source documents, however, if the AE meets the criteria of an SAE. To ensure patient safety, every SAE (see Supplemental 3 for definition), regardless of suspected causality, occurring after the patient has provided informed consent and after the patient begins taking study drug and until 30 days after the patient has stopped study participation will be recorded and reported to Incyte. Any SAEs experienced after this 30-day period should only be reported to Incyte if the investigator suspects a causal relationship to the study drug. All malignant neoplasms will be assessed as serious under "medically significant" if other seriousness criteria are not met. Medical and scientific judgment will be exercised in deciding whether other situations should be considered serious reactions, such as important medical events that might not be immediately life threatening or result in death or hospitalization but might jeopardize the patient or might require intervention to prevent one of the outcomes listed in SAE. Any suspected transmission via a medicinal product of an infectious agent is also considered a serious adverse reaction. All AEs (serious and non-serious) are captured and recorded, SAEs also require individual reporting (see Supplemental 3). To ensure patient safety, each pregnancy occurring while the patient is on study treatment must be reported to the sponsor-investigator within 24 hours of learning of its occurrence. The pregnancy should be followed up to determine outcome, including spontaneous or voluntary termination, details of the birth, and the presence or absence of any birth defects, congenital abnormalities, or maternal and/or newborn complications. Pregnancy follow-up should be recorded on the same form and should include an assessment of the possible relationship to the study treatment. Any SAE experienced during the pregnancy and unrelated to the pregnancy must be reported on a SAE form.
